5.2 Exclusion Criteria

Participants are excluded from the study if any of the following criteria apply:

1. ≥ 3 previously failed cycles of ET
2. Participants with diseases that cannot tolerate pregnancy
3. Hydrosalpinx
4. Severe endometriosis (Endometriosis American Society for Reproductive Medicine (ASRM) criteria from 1996)

5. Known hypersensitivity to progesterone, the excipients of Crinone® and Duphaston®
6. Vaginal bleeding of unknown origin
7. History of recurrent miscarriages
8. Vaginitis
9. Thromboembolic diseases (thrombophlebitis, thromboembolic disorder, or cerebral apoplexy) or patients with an history of these conditions
10. Known or suspected progestogen-dependent neoplasm
11. Participation in another clinical trial within the past 30 days
12. Contraindications of both Crinone® and Duphaston®
13. Participants with potential risk (The participants/partner are from high risk region which can be tracked by health barcode) or symptoms of COVID-19 (eg. fever, cough etc).

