4.1 Overall Design

This is a Phase IV, local, single center, open label, pilot, randomized controlled clinical study to compare the efficacy and safety of Crinone® versus combination medication. The study population are infertile women who receive FET in ACs. This study plans on including 334 participants from a single reproductive center over 25 months. Participants that enter the study will be randomized into either of the two groups. The study intervention drug received by the participant is determined based on the result of randomization. The randomization procedure is described in [Section 6.3](#). The overall scheme of the study is in [Section 1.2](#) and the Schedule of Activities at each visit can be found in [Section 1.3](#).

The participants will sign an ICF; the participants are free to withdraw at any time without prejudice to their medical care, and they are not obliged to state their reasons for withdrawal. Upon site initiation, the Investigator site will enroll the eligible participants who meet the inclusion and none of the exclusion criteria in a consecutive manner until the enrollment target is reached. The study will consist of a screening period, followed closely by procedures from endometrial transformation to ongoing pregnancy assessment, which lasts for approximately 75 days. Study treatment will start from the day of endometrial transformation (Day -5) until ongoing pregnancy assessment, which occurs between 10-12 weeks of pregnancy (8-10 weeks after ET). The middle number of 9 weeks (Day 63) after ET is used to define the study day with a window of 10 days on each side as leeway. The treatment will be administered for approximately 75 days.

Relevant data according to study requirements will be recorded in standard CRF. When the study starts, this reproductive center will include participants who enter the cycle. The information of the qualified yet excluded participants who have signed ICFs will be recorded, and the reason for their exclusion will also be recorded in the CRF. If a participant has entered the study and later discontinue their study intervention, the reason for discontinuing the study intervention will be recorded in the CRF.

[figure not shown]
Participant follow-up will occur until her ongoing pregnancy is confirmed and/or until End of Study (defined in [Section 4.4](#)).

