4.4 End of Study Definition

A participant has completed the study if she has completed all study parts, including the last visit or the last scheduled procedure shown in [Section 1.3](#) (Schedule of Activities).

The end of the study is defined as the date of the last visit of the last participant or the last scheduled procedure shown in [Section 1.3](#) (Schedule of Activities) for the last participant in the study.

The date and the reason for the completion / withdrawal from the study intervention or study (see [Section 7](#)) will be collected.

5 Study Population

The criteria in [Sections 5.1](#) (Inclusion Criteria) and [5.2](#) (Exclusion Criteria) are designed to enroll only participants, who are appropriate for the study; thereby, ensuring the study fulfills its objectives. All relevant medical and nonmedical conditions should be taken into consideration when deciding whether a participant is suitable for this study.

Prospective approval of protocol deviations to inclusion and exclusion criteria, also known as protocol waivers or exemptions, are not permitted.

Before performing any study assessments that are not part of the participant's routine medical care, the Investigator will confirm that the participant or the participant's legal representative has provided written informed consent, as indicated in [Appendix 2](#) (Study Governance).

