6.3 Measures to Minimize Bias: Study Intervention Assignment and Blinding

6.3.1 Study Intervention Assignment

Participants will be randomized in a 1:1 ratio to receive either Crinone® or the combination medication group on the day of ET.

The trial is designed as a single center trial, and randomization will be conducted on the ET day by using the block permutation method and stratified by age group (ages 20 to 35 years, or ages 35 years and over), which will guarantee that a balanced number of participants will be obtained between Crinone® and the combination medication groups inside each age stratum. If an error occurs (for example if the wrong list is used), the participant should continue with their assigned study intervention, and the next participant should still be assigned the next available number and study intervention of the correct list. The site must not attempt to “correct” for the error (i.e., if a participant is on the Crinone® list instead of the

combination medication group list, the site must not try to assign the Crinone® participant to the combination medication group list to offset this). Since ACCESS is an open-labeled observational study, baseline characteristic analysis will be presented to show whether the participants were well-stratified by age between the two study intervention groups.

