Appendix 4 Visit Procedures

All participants' data will be collected in anonymity. The participants are assigned to the two study intervention groups at the ratio of 1:1 using a permuted block randomization according to a randomization schedule generated by the statistician using a computer program. Each participant will have a unique participant number assigned to her and this will be referenced throughout the study as the participant's identifier. The Investigator should keep a separate code identification list with all the participants' information to be retained at the site. Details of randomization are in [Section 6.3](#).

After randomization, the participants will receive either Crinone® or Crinone® in combination with Duphaston® for luteal phase support in FET AC.

The data collection time points for the two protocols are as follows:

1. Screening/Baseline
2. Endometrial transformation day
3. ET day
4. β -hCG test: Serum β -hCG test 13 to 15 days after ET
5. Clinical Pregnancy Assessment: Ultrasound examination 4 to 6 weeks after ET
6. Ongoing Pregnancy Assessment (presence of viable fetus at 10-12 weeks of pregnancy [8-10 weeks after ET])

All procedures described in [Appendix 4](#) will be conducted according to the routine practices of the study site.

Visit 1 (baseline evaluation):

The participant will be informed of the study objectives and overall requirements at the initial study visit and written informed consent will be obtained prior to any study-specific assessments. Participants may have already initiated estradiol valerate use. The participant will then undergo a brief clinical evaluation to ensure compliance with the inclusion and exclusion criteria to determine eligibility (see [Section 5](#)).

Data for all participants will come from the participants' screening or baseline visits and the participants' medical records.

The following must be completed at Visit 1:

- Visit date
- Participant name will be recorded and kept confidentially in the clinic solely for the purposes of generating a unique participant number, which will be used to identify each participant in the study anonymously.

- Demographics include age, gender and date of birth
- Physical exam and vital signs
- Weight and height
- Clinical and gynecological examination (pelvic examination will be performed); examinations from medical history prior to signing the ICF is also accepted per the Investigator's decision

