- Gynecological history: duration of infertility, menstrual cycle, history of miscarriages, history of pelvic surgery, history of ovarian surgery.
- Medical history and concomitant illness
- Any concomitant medication taken by the participant when entering the study
- Concomitant medications prescribed and reasons
- Ultrasound without abnormal findings (endometrium thickness will be measured); examinations from medical history prior to the initiation of estradiol valerate before signing the ICF is also accepted per the Investigators decision
- Serum β -hCG levels must be negative; examinations from medical history prior to signing the ICF is also accepted per the Investigators decision
- Check I/E criteria
- Date of initiation of estradiol valerate (if applicable)
- Initial dose of estradiol valerate (if applicable)
- Details of dose adjustments of estradiol valerate if any (if applicable)
- Duration and total dosage of estradiol valerate (if applicable)

Visit 2 (endometrial transformation day)

The participants should come to the clinic to measure their endometrial thickness on endometrial transformation day. Should the endometrial thickness be ≥ 8 mm, Crinone® will be administered at a dose of 90 mg/d for 4-6 days to assist the secretory transformation of the endometrium. The following data will be collected:

- Date of initiation of estradiol valerate
- Initial dose of estradiol valerate
- Details of dose adjustments of estradiol valerate if any
- Duration and total dosage of estradiol valerate
- Date of initiation of Crinone®

- Endometrial thickness before initiation of Crinone® (Endometrial thickness will be measured by ultrasound. However, if the ultrasound was performed on the endometrial transformation day prior to signing the ICF, a new ultrasound is not required.)
- Check I/E criteria
- Recording of AEs
- Concomitant medications prescribed and reasons.

The total duration of estradiol valerate before the endometrial transformation should be no more than 20 days.

Visit 3 (embryo transfer day)

After 4-6 days of assisted secretory transformation of the endometrium, no more than two D5 embryos will be transferred on the fifth, sixth, or seventh day. After randomization, the luteal phase support study intervention will be initiated.

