- Study intervention A (Crinone® group): Randomized participants will be given Progesterone gel 8% (Crinone®) 90 mg/p.v./q.d from the day of endometrial transformation. It will be suggested that they administer the drug in the morning and at the same time of day throughout the trial. A β -hCG test will be done 14 days after ET. If serum β -hCG levels are negative, the study will be discontinued. If the result of the β -hCG test is positive, Crinone® administration will continue with the above regimen. At 35 days after ET, an ultrasound will be done to detect the number of gestational sacs to confirm the results of clinical pregnancy. If clinical pregnancy is positive, continue Crinone® administration until ongoing pregnancy assessment. Should a miscarriage occur at any point, Crinone® administration will be discontinued.
- Study intervention B (Crinone® + Duphaston® group): Randomized participants will be given Progesterone gel 8% (Crinone®) 90 mg/p.v./q.d from the day of endometrial transformation, following which Duphaston® at 10 mg/p.o./bid will be administered from the day of ET. It will be suggested that they administer the drugs in the morning and at the same time of day throughout the trial. A β -hCG test will be done 14 days after ET. If serum β -hCG levels are negative, the study will be discontinued. If the result of the β -hCG test is positive, the combination medication will continue with the above regimen. At 35 days after ET, an ultrasound will be done to detect the number of gestational sacs to confirm the results of clinical pregnancy. If clinical pregnancy is positive, continue combination medication until ongoing pregnancy assessment. Should a miscarriage occur at any point, combination medication will be discontinued.

All participants will receive oral estradiol valerate continuously and the dose of estradiol valerate will be adjusted according to local practices.

The following data will be collected:

- Duration and total dosage of estradiol valerate

- Date of ET
- Number of embryo(s) transferred (no more than 2)
- Embryo quality
- Check I/E criteria
- Recording of AEs
- Concomitant medications prescribed and reasons.

Visit 4 (β -hCG positive assessment)

Participants treated by ART are routinely monitored for early detection of pregnancy by measuring serum β -hCG concentration according to the site's routine clinical practices.

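### Exclusion 12, read literally, bars only women contraindicated to both products, although every woman is given Crinone and may be allocated to Duphaston as well

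*Protocol*

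**What the plan says.** The exclusion list in Protocol Section 5.2 works item by item: "Participants are excluded from the study if any of the following criteria apply". Item 12 is the only general contraindication criterion, and it reads "Contraindications of both Crinone® and Duphaston". Items 5, 6, 9 and 10 separately name hypersensitivity, unexplained vaginal bleeding, thromboembolic disease and progestogen-dependent tumours.

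On treatment, Protocol Section 4.1 says "Participants that enter the study will be randomized into either of the two groups", and Section 6.3.1 says "Participants will be randomized in a 1:1 ratio to receive either Crinone® or the combination medication group on the day of ET". Appendix 4 describes the arms: "After randomization, the participants will receive either Crinone® or Crinone® in combination with Duphaston® for luteal phase support in FET AC". Crinone comes first. At Visit 2, "Should the endometrial thickness be ≥ 8 mm, Crinone® will be administered at a dose of 90 mg/d for 4-6 days", and embryo transfer and randomisation follow at Visit 3. In the combination arm Crinone is given from the transformation day, "following which Duphaston® at 10 mg/p.o./bid will be administered from the day of ET".

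Neither document says that *both* in item 12 is to be taken as *either*.

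**The concern.** A 1:1 randomised comparison requires that each woman could properly be given whichever regimen she draws. Here that means she must be able to take Crinone, which nobody avoids, and must also be able to take Duphaston, which she may draw. Item 12 is the criterion that should secure this. Taken at its word, it requires two contraindications before it excludes anyone, so a woman with one contraindication passes.

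What is at stake is mainly safety: possible exposure to a product that is contraindicated for the woman concerned. Detection is a second, smaller matter. SAP Section 8.1 counts departures from the eligibility criteria as important protocol deviations. Under the literal wording such a woman meets the criteria, so her enrolment would not be recorded as an eligibility deviation.

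**Working it through.** No sample size, power or interval figure is involved, so the check sets the eligibility wording beside the treatment plan.

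**Inputs**
- Item 12 as worded: a joint condition on the two products (Protocol 5.2).
- One applicable item is enough to exclude (Protocol 5.2, opening line), so the word *both* inside item 12 fixes how far that item reaches.
- Allocation 1:1, that is 0.5 to each arm (Protocol 6.3.1).
- Crinone in both arms, started at Visit 2; Duphaston in the combination arm only, from the day of transfer (Protocol Appendix 4).

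**Step 1: whom item 12 excludes under each reading**

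| Contraindicated to | Literal reading (Crinone AND Duphaston) | Loose reading (Crinone OR Duphaston) |
|---|---|---|
| Neither | not excluded | not excluded |
| Crinone only | not excluded | excluded |
| Duphaston only | not excluded | excluded |
| Both | excluded | excluded |

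The readings differ in the two middle rows.

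**Step 2: what a woman in those rows would be given, if no other item or judgement excludes her**
- Chance of receiving Crinone = 0.5 × 1 (Crinone arm) + 0.5 × 1 (combination arm) = 1. She would already be receiving it from Visit 2, before any allocation.
- Chance of allocation to Duphaston = 0.5 × 0 (Crinone arm) + 0.5 × 1 (combination arm) = 0.5.

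The Crinone-only case is therefore the sharper one. Its timing also matters. The Schedule of Activities (Protocol 1.3) repeats the eligibility check at Visits 1, 2 and 3, but by Visit 3 Crinone has been in use for several days, and each check applies the same wording.

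**Step 3: do the other items close the gap?**
Items 5, 6, 9 and 10 exclude particular conditions whichever product they bear on. They would close the gap only if, between them, they covered every contraindication to each product. That cannot be settled here, because the package inserts are not part of the documents. Item 5 is itself loosely built. Its list can be read as the excipients of both products, or as the excipients of Crinone together with Duphaston itself.

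**Step 4: is the literal reading contrived?**
For these same two drugs, SAP Section 15.1.1 tabulates events related to either drug separately from events related to both. SAP Section 15.1.2 explains at least one study intervention as either of the two. The study's own analysis plan thus treats the two words as different, so a reader who takes *both* as joint is following the study's usage.

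**The case against.** The strongest reply is that the literal reading is not what was meant. Item 12 speaks of contraindications *of* the two products, which can be read as the contraindications belonging to each. Item 5 uses similarly loose list grammar, and few readers would take it to demand hypersensitivity to the excipients of both products. This stands as to intent, and the loose reading is probably the right one. It does not settle the text, which a site has to apply without a gloss.

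Other safeguards also exist. The introduction to Protocol Section 5 asks that all pertinent conditions be weighed in judging suitability. Inclusion 7 requires that the woman be able to complete the study. Duphaston is prescribed by the investigator (Sections 6.1 and 6.4), so a physician stands between allocation and the tablet. All of this makes exposure less likely. None of it is a specific contraindication criterion, and the prescribing step protects only against Duphaston, not against the Crinone that starts at Visit 2.

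Two stronger readings are tempting, and the documents support neither.
- A reader might infer from "Prospective approval of protocol deviations to inclusion and exclusion criteria, also known as protocol waivers or exemptions, are not permitted" that sites are bound to item 12 exactly as worded and must enrol anyone who passes it. That sentence forbids admitting women who fail the criteria. It does not oblige a site to enrol every woman who meets them, and the sentence before it calls for a wider suitability judgement.
- A reader might infer a bias in the comparison, because a woman who cannot take Duphaston could depart from her allocation for that reason only in the combination arm. The mechanism is possible, but the documents give no frequency and no basis for calculating an effect on the ITT or PP result. With probably few such women among the 334 planned, in a pilot with no confirmatory testing, any effect is likely negligible.

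**Conclusion.** The point holds as a defect in operative eligibility wording: taken literally, item 12 does not match a design in which everyone receives Crinone and half are allocated to Duphaston as well. For a woman with a single-product contraindication that nothing else catches, the chance of being given the product is 1 for Crinone, and the chance of being allocated to it is 0.5 for Duphaston.

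This rests on the literal reading, which is probably not the intended one, and on there being some single-product contraindication outside items 5, 6, 9 and 10 and the general suitability judgement. The documents neither show nor rule out such a contraindication. The number of women affected cannot be determined and is probably small. Nothing here shows that any such woman was enrolled. The point is minor, and worth making because it concerns participant safety and costs almost nothing to settle.

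**What to change.** Ask the sponsor to reconcile exclusion 12, and the loosely worded list in exclusion 5, with the arm descriptions in Protocol Appendix 4. The resulting text should leave no doubt that every woman must be eligible for either allocation, and that this is established before Crinone starts at Visit 2 as well as before randomisation at Visit 3. The clinical content of the contraindications is for the sponsor and the investigator to state.

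The cost is a short wording change in the next amendment. The downside is that a few women may become ineligible; that is an assumption, since the documents give no frequency. No analysis, estimate or planned number of participants needs to change.

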5.3 Lifestyle Considerations

Not applicable

5.4 Screen Failures

Individuals who do not meet the criteria for participation in this study (screen failure) may not be rescreened.

6 Study Interventions

Study intervention is any investigational intervention(s), marketed product(s), placebo, or medical device(s) intended to be administered to a study participant per the study protocol.

6.1 Study Interventions Administration

Study Intervention Name:	Crinone®	Duphaston®
Dose Formulation:	Progesterone gel 8% (90 mg)	Tablet
Unit Dose Strength(s)/Dosage Level(s):	90 mg	10 mg/tablet
Route of Administration:	Intravaginal	Oral
Dosing Instructions:	1 gel, q.d. in the morning	1 tablet, b.i.d
Supplier/Manufacturer:	Merck will provide Crinone® for free	Prescribed for participants in the clinic by Investigators
Packaging and Labeling	
every box contains 15 applicatorsThe validity period is 36 monthsEach applicator will be packaged and labeled per all applicable regulatory requirements and Good Manufacturing Practice Guidelines.	
According to the package labelling as prescribed by the Investigator

6.2 Study Interventions Preparation, Handling, Storage, and Accountability

The Investigator, institution, or the head of the medical institution (where applicable) is responsible for study intervention accountability, reconciliation, and record maintenance (i.e., receipt, reconciliation, and final disposition records).

- Upon receipt of the study intervention(s), the Investigator or designee must confirm appropriate temperature conditions have been maintained during transit and any discrepancies are reported and resolved before use. Also, the responsible person will check for accurate delivery and acknowledge receipt by signing or initialing and dating the appropriate document and returning it to the location specified. A copy will be archived for the Investigator Site File.

- Only participants enrolled in the study may receive study intervention(s) and only authorized site staff may supply it. All study intervention(s) must be stored in a secure, environmentally-controlled, and monitored (manual or automated) area, in accordance with the labeled storage conditions, and with access limited to the Investigator and authorized site staff.
- Dispensing will be recorded on the appropriate accountability forms so that accurate records will be available for verification at each monitoring visit.
- Study intervention(s) accountability records at the study site will include the following:
 - Confirmation of receipt, in good condition and in the defined temperature range.
 - The inventory provided for the clinical study and prepared at the site.
 - The dose(s) each participant used during the study.
 - The disposition (including return, if applicable) of any unused study intervention(s).
 - Dates, quantities, batch numbers, expiry dates, and the participant numbers.
- The Investigator site will maintain records, which adequately documents that participants were provided the doses specified in this protocol, and all study intervention(s) provided were fully reconciled.
- Unused study intervention(s) must not be discarded or used for any purpose other than the present study. No study intervention that is dispensed to a participant may be re-dispensed to a different participant.
- A Study Monitor will periodically collect the study intervention(s) accountability forms.
- Further guidance and information for the final disposition of unused study intervention(s) are provided in the Study Reference Manual.

